## 9.2 Clinical Laboratory Evaluation

### 9.2.1 Hematology and Biochemistry

Hematology and biochemistry safety parameters are measured at Visit 1 (screening), Visit 5, Visit 6, Visit 7, Visit 8 (for patients taking valproic acid only) and Visit 9 (end of treatment).

Summaries will be presented by treatment group for each laboratory parameter at each visit. Change from baseline and percent change from baseline to each post-baseline visit will also be presented.

If values for any of the parameters are below or above the limit of quantification of the assay (BLQ or ALQ), then they will be included in the summary tables at the BLQ or ALQ thresholds.

Where laboratory samples are repeated, the baseline value is defined as the final recorded value prior to the first dose of IMP.

Shift tables for hematology and biochemistry parameters will be produced, based upon normal ranges and GW toxicity limits (See [Appendix 4](#)), to determine the categorical shifts from baseline to each post-baseline visit. Values will be categorized as ‘Normal’, ‘Low’ or ‘High’ based on normal ranges and ‘Toxicologically Low’, ‘Toxicologically Normal’ or ‘Toxicologically High’ based on GW toxicity limits.

For eGFR, results will be assigned to the following grades:

- Normal:  $>60$  ml/min/1.73 m^2
- Grade 1:  $60$  ml/min/1.73 m^2
- Grade 2:  $\geq 30$  and  $<60$  ml/min/1.73 m^2
- Grade 3:  $\geq 15$  and  $<30$  ml/min/1.73 m^2
- Grade 4:  $<15$  ml/min/1.73 m^2

A separate shift table will be produced for eGFR based upon the above grades to determine the categorical shifts from baseline to each post-baseline visit.

An additional table will be produced, summarizing the number of patients meeting the following criteria:

- Alanine aminotransferase (ALT)  $> 1 \times$ ULN at baseline
- Aspartate aminotransferase (AST)  $> 1 \times$ ULN at baseline
- AT  $> 1 \times$ ULN at baseline
- Treatment-emergent ALT  $> 3 \times$ ULN,  $> 5 \times$ ULN and  $> 8 \times$ ULN
- Treatment-emergent AST  $> 3 \times$ ULN,  $> 5 \times$ ULN and  $> 8 \times$ ULN
- Treatment-emergent AT  $> 3 \times$ ULN,  $> 5 \times$ ULN and  $> 8 \times$ ULN
- Treatment-emergent AT  $> 3 \times$ ULN and either bilirubin  $> 2 \times$ ULN or INR  $> 1.5$

where AT is AST or ALT, and treatment emergent is defined as criteria not met at baseline, but met at any time post-baseline. For each of these parameters, a patient with value  $> 8$  ULN will also fall into the  $>3$  and  $>5$  ULN categories.

The above will be summarized overall and for the following subgroups:

- Valproic acid use (as a concomitant medication) (Yes, No).
- Clobazam use (as a concomitant medication) (Yes, No).
- Valproic acid use and Clobazam use (as concomitant medications) (Yes/Yes, Yes/No, No/Yes, No/No).  
(A medication will be considered concomitant if it has a start date on or after the first dose of IMP or if it was started prior to the first dose of IMP and was ongoing.)
- Patients taking 3 or more current AEDs.
- Patients taking 4 or more current AEDs.

All laboratory data will be listed; listings will include limited demographic information about the patient (age, sex, race and weight at baseline). Abnormal laboratory values will be listed separately. A further listing will be created for the laboratory reference ranges and toxicity limits. A listing of liver parameters (ALT, AST, bilirubin and INR) will be produced that includes the baseline result, result at the particular visit, change from baseline, upper limit of normal (ULN) value, ratio of result to baseline and ratio of result to ULN.

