9.1.3 Unscheduled Visits

Unscheduled visits and assessments may be performed in the event of a safety concern, as deemed necessary by the investigator. Data from any unscheduled visits should be reported on the unscheduled visits eCRF.

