Aspartate aminotransferase	Mean corpuscular hemoglobin	pH		
Calcium	Platelets	Protein		
Creatine kinase	Red blood cell count	White blood cells		
Creatinine	White blood cell count with automated differential	Bilirubin		
Creatinine clearance		Ketones		
Gamma-glutamyl transferase		Specific gravity		
Glucose		Urobilinogen		
Human chorionic gonadotropin				
HDL-cholesterol				
IGF-1*				
Potassium				
Prolactin				
Prothrombin time (plasma)				
Sodium				
Total bilirubin				
Total protein				
Triglycerides				
Urea (blood urea nitrogen)				

*Visits 1 and 9 only; IGF-1 laboratory results to remain blinded throughout the trial.

¹Dipstick at site or analysed at a central laboratory.²Analysed at the trial site by use of a dipstick (if allowed per local regulations).

HDL = high density lipoprotein

Investigators at trial sites will be notified of laboratory test results. All laboratory results will be reviewed, and the reports signed and dated by an investigator. Any results considered to be of clinical significance must be addressed and followed up as clinically appropriate. The results of THC screening will be reported back to the study site to permit confirmation of eligibility. All laboratory results considered to represent an AE must be documented on the eCRF. For reporting and follow-up of potential cases of drug-induced liver injury, see [Section 12.8](#).

Study Code: GWND18064

EudraCT Number: 2018-003370-27

Clinical Protocol 4.1, 07Jul2020 (duplicate synopsis removed)

Repeat samples will be taken, if required, for clinical follow-up or if the sample is lost or damaged. Any abnormal end of treatment clinical laboratory result of clinical significance must be repeated at regular intervals until it returns to normal, or until an investigator is satisfied that the abnormality is not related to the IMP and needs no further investigation. Blood sample volume requirements and processing procedures will be detailed in a separate laboratory manual; the maximum cumulative amount of blood taken in any 4-week period, including PK blood samples, will be 2.55 mL/kg of body weight and will not exceed a total of 50 mL within any 8 week period⁶⁷, taking into account possible repeat tests. The patient/caregiver must be advised that it may not be safe for the patient to undertake further blood tests within 1 month of any trial-related blood draws and to inform the investigator if they suffered any blood loss during the 1-month period leading up to a planned blood draw.

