**Table 3**      **Study Visits**

Actual Visit	Visit Label
Visit 1: Screening	Screening
Visit 2: Day 1, baseline visit	Day 1
Visit 3: Day 8	Day 8
Visit 4: Day 15	Day 15
Visit 5: Day 29	Day 29
Visit 6: Day 57	Day 57
Visit 7: Day 85	Day 85
Visit 8: Day 127	Day 127
Visit 9: Day 169	End of Treatment
Visit 10: Day 179	End of Taper
Visit 11: Day 207	Safety Follow-Up

No derivation will be used for visits; data will be tabulated and listed according to the visit it was recorded under in eCRF.

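### SAP 9.2.1 gives no rule for unscheduled or repeat post-baseline laboratory values and, outside the ALT/AST-based table, no any-time toxicity count, so some toxic values may reach only the listings

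*SAP*

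**What the plan says.** SAP 9.2.1 organises the general laboratory output by visit. For the descriptive tables: "Summaries will be presented by treatment group for each laboratory parameter at each visit". The shift tables, whether by normal range, by the GW toxicity limits of Appendix 4 or by eGFR grade, are produced "to determine the categorical shifts from baseline to each post-baseline visit". The sampling visits are given in the same section: "Hematology and biochemistry safety parameters are measured at Visit 1 (screening), Visit 5, Visit 6, Visit 7, Visit 8" (the last only for patients on valproic acid), and Visit 9.

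On allocating data to visits, SAP 6.1.1 (under Table 3) says: "No derivation will be used for visits; data will be tabulated and listed according to the visit it was recorded under in eCRF". The labels in Table 3 run from Screening to Safety Follow-Up, and none is for an unscheduled visit.

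Protocol 9.1.3 sends off-schedule data to a separate page: "Data from any unscheduled visits should be reported on the unscheduled visits eCRF". Protocol 9.2.10 expects extra samples: "Repeat samples will be taken, if required, for clinical follow-up or if the sample is lost or damaged". The only repeat-sample rule in SAP 9.2.1 concerns baseline, where the final value before first dose is used.

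SAP 9.2.1 adds one table with any-time logic. It counts patients who did not meet a criterion at baseline but met it at some point afterwards. The criteria are ALT, AST, or either enzyme above 3, 5 and 8 × ULN, and either enzyme above 3 × ULN combined with bilirubin above 2 × ULN or INR above 1.5. All laboratory values are listed, and abnormal ones are listed again separately.

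**The concern.** Off-schedule blood samples are often taken because something looked wrong or an abnormal result needed follow-up. If the tables have no place for them, a patient can reach a toxic value, recover by the next scheduled visit, and show as normal in every laboratory shift table. The Appendix 4 limits exist to give a count that does not depend on clinical judgement, and that count is what would be lost. SAP Sections 1 and 8 make the whole analysis descriptive, so the safety tables are a main product of the trial.

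**Working it through.** The plan states no figure to reproduce, and no power or error-rate calculation applies. The check sets the provisions side by side and then takes the sampling gap from the schedule.

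**1. Which summaries count a patient at any time after baseline?**

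| Data | By-visit summary or shift | Any-time post-baseline patient count |
|---|---|---|
| Vital signs (SAP 9.3.1, Appendix 3) | Yes | Yes, at least one flagged value |
| ECG (SAP 9.3.2, Appendix 3) | Yes | Yes, at least one flagged value |
| ALT, AST (SAP 9.2.1) | Yes | Yes |
| Bilirubin, INR (SAP 9.2.1) | Yes | Only jointly with ALT or AST above 3 × ULN |
| Isolated bilirubin, alkaline phosphatase, gamma GT, sodium, potassium, creatinine (Table 11) | Yes | None |
| eGFR grade (SAP 9.2.1) | Yes | None |
| Hemoglobin, platelets, white cells, neutrophils (Table 12) | Yes | None |

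The SAP uses any-time logic for vital signs, ECG and the ALT/AST-based criteria. It does not use it for the remaining laboratory toxicity limits, and gives no reason.

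**2. Where does an off-schedule value go?** Protocol 9.1.3 records it on the unscheduled visits eCRF. SAP 6.1.1 tabulates it under the visit recorded there, without re-mapping. Table 3 has no label for that visit. The documents do not say whether a repeat of a scheduled sample is entered under the scheduled visit or on the unscheduled page. They also do not say which of two post-baseline values at one visit is tabulated.

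**3. Are such samples expected?** Yes. Besides the general provision for repeats, Protocol 9.2.10 requires a clinically significant abnormal end-of-treatment result to be repeated until it normalises or is judged unrelated. Protocol 12.8 calls for repeat testing when total bilirubin alone exceeds 2 × ULN. That is also the Table 11 toxicity limit for bilirubin, and taken alone it has no any-time count.

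**4. How long are the gaps between scheduled samples?** Visit days are from Protocol Appendix 1.

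- Not on valproic acid: Days 29, 57, 85 and 169. Gaps from Day 1: 29 − 1 = 28; 57 − 29 = 28; 85 − 57 = 28; 169 − 85 = 84 days.
- On valproic acid: Day 127 is added, so the last gap splits into 127 − 85 = 42 and 169 − 127 = 42 days.
- Treatment lasts 169 − 1 = 168 days. For patients not on valproic acid the last gap is 84/168 = 50% of it.
- No safety laboratory sample is scheduled at Visit 10 or 11.

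**5. Trace one case.** A patient not on valproic acid has a platelet count at or below the Table 12 limit of 74 × 10⁹/L at an unscheduled sample on a day between Visits 7 and 9, and normal counts at both of those visits. The Visit 7 and Visit 9 shift rows show normal. No any-time table covers platelets. The value is in the full listing and the abnormal listing. It enters a summary by arm only if the investigator reports it as an adverse event, or if the table programs add an unscheduled row that the SAP does not mention.

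**The case against.** Three arguments on the other side carry weight.

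First, a reader might infer that the SAP restricts these tables to scheduled visits. It does not say so. Tabulating by eCRF visit is compatible with an added unscheduled row, Table 3 is a labelling convention, and the table shells are a separate document that was not available. This stands: the SAP is silent and does not exclude these values.

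Second, a reader might infer that an off-schedule toxic value vanishes from all summaries. That goes too far. Protocol 9.2.10 requires laboratory results considered to represent an adverse event to be recorded, and SAP 9.1 then counts them among the TEAEs. Every value is also listed. This stands as well, but the adverse-event route depends on investigator judgement and listings give no count by arm.

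Third, a reader might infer that every toxic value between Day 85 and Day 169 in a patient not on valproic acid must be off schedule. Protocol 9.1.1.7 makes Visit 9 the withdrawal visit too, with hematology and biochemistry taken, so an early withdrawal in that interval yields a Visit 9 sample. The long gap is also a feature of protocol sampling, and a worst-value table adds no samples.

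There is no conflict with the protocol either: its Section 13.6.3.4 asks for summaries and shift tables, and the SAP supplies them.

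**Conclusion.** The point holds as a reporting gap. The SAP lacks a rule for unscheduled and repeat post-baseline laboratory values. Outside the ALT/AST-based table, no laboratory summary counts patients with a toxic value at any time. A transient toxic hematology, electrolyte, creatinine or eGFR, alkaline phosphatase, gamma GT or isolated bilirubin value seen only at an extra sample may be left to the listings unless it is reported as an adverse event.

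The exposed interval is known, but the number of patients is not. The documents give no rate of off-schedule toxic values, and the trial was discontinued, so planned arm sizes are no guide. Omitting such values can lower or leave unchanged the count of affected patients in an arm, but cannot raise it. A reader might infer that the comparison between arms is therefore biased toward no drug effect. The documents do not show this, because undercounting could occur in every arm.

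The conclusion assumes that the unseen table shells do not already contain a worst-value or unscheduled row. No hypothesis test is affected. The change is worth making because it is cheap and extends what the SAP already does for vital signs and ECG.

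**What to change.** Keep the by-visit tables and add to SAP 9.2.1:

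1. For each parameter, a shift from baseline to the worst post-baseline value, lowest and highest separately, by normal range and by toxicity category. For eGFR, a shift to the worst grade.
2. For each parameter with an Appendix 4 limit, the number of patients per arm with at least one post-baseline value in the toxic range.
3. A statement that items 1 and 2 use all scheduled, unscheduled and repeat samples.
4. A rule for which value the by-visit tables use when a visit has repeats.
5. A footnote that patients sampled more often have more chances to be flagged.

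The cost is a derived worst-value record in each direction per parameter, the added rows and two sentences of text. The data are already collected. The one drawback is unequal sampling between patients, which the footnote discloses. The SAP plans no blinded data review meeting (Section 4.2.2), so the rule should be written into the SAP before unblinding.

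### The eGFR grades in SAP 9.2.1 reduce Grade 1 to the single value 60, so the separate eGFR shift table cannot show any fall that stays above 60

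*SAP*

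**What the plan says.** SAP 9.2.1 (Hematology and Biochemistry) gives five eGFR categories. The top three are "Normal: $>60$ ml/min/1.73 m"², "Grade 1: $60$ ml/min/1.73 m"² and "Grade 2: $\geq 30$ and $<60$ ml/min/1.73 m"². Grade 3 runs from 15 to below 30, and Grade 4 is below 15. The SAP then states: "A separate shift table will be produced for eGFR based upon the above grades to determine the categorical shifts from baseline".

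The same section plans other laboratory outputs:
- By-visit summaries for each parameter: "Change from baseline and percent change from baseline to each post-baseline visit will also be presented".
- General shift tables: "Shift tables for hematology and biochemistry parameters will be produced, based upon normal ranges and GW toxicity limits".
- Listings: "All laboratory data will be listed; listings will include limited demographic information about the patient". Abnormal values are also listed separately.

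Protocol Table 9.2.10-1 sets the biochemistry panel. It includes creatinine and "Creatinine clearance", but not eGFR. The derived-variables section of the SAP (6.1.9) gives no eGFR formula.

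**The concern.** A graded shift table is meant to show movement between levels, including the first step away from normal. Here the first abnormal level has no width. A patient can lose a large share of baseline eGFR and stay in the Normal row and column. A patient starting just above 60 can lose little and appear as Grade 2. A reader who takes the table at face value would see an empty or nearly empty Grade 1 and could conclude that no mild change occurred, when the table had no means of showing it.

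The second difficulty is the input. If eGFR is not reported by the laboratory, it has to be derived. The SAP names neither a formula nor a rule for the measurements the formula would need, so two programmers could produce different tables from the same data.

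**Working it through.** No sample size or error rate is involved, and the plan gives no figure to reproduce. The check takes the printed limits as written, all from SAP 9.2.1.

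**Step 1: coverage and width.** Assign every value from 0 to 150 ml/min/1.73 m² to a category. The upper end of 150 is an arbitrary choice for the check.

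| Category | Limit as printed | Whole numbers 0–150 | Steps of 0.1 |
|---|---|---|---|
| Normal | > 60 | 90 | 900 |
| Grade 1 | 60 | 1 | 1 |
| Grade 2 | ≥ 30 and < 60 | 30 | 300 |
| Grade 3 | ≥ 15 and < 30 | 15 | 150 |
| Grade 4 | < 15 | 15 | 150 |
| Total | | 151 | 1501 |

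Every value falls in exactly one category, so the rule can be programmed as it stands. Grade 1 holds 1 of 151 whole-number values, or 1 of 1501 at one decimal place.

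**Step 2: how falls are tabulated.** Percentage change = 100 × (post − baseline) / baseline. The values are illustrations, not data from the trial.

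| Baseline → post | Change | Shift shown |
|---|---|---|
| 120 → 90 | −25.0% | Normal → Normal |
| 120 → 75 | −37.5% | Normal → Normal |
| 90 → 61 | −32.2% | Normal → Normal |
| 120 → 61 | −49.2% | Normal → Normal |
| 120 → 60 | −50.0% | Normal → Grade 1 |
| 120 → 59.9 | −50.1% | Normal → Grade 2 |
| 65 → 59 | −9.2% | Normal → Grade 2 |

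**Step 3: could a missing comparison sign explain it?** Grade 1 is printed without an operator. Try each one against the printed limits of the other categories:
- ≥ 60 overlaps all of Normal, and only 60 belongs to Grade 1 alone.
- ≤ 60 overlaps Grades 2 to 4, and again only 60 belongs to Grade 1 alone.
- < 60 overlaps Grades 2 to 4 and leaves no value unique to Grade 1.
- > 60 overlaps Normal and leaves no value unique to Grade 1.

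The limits of Normal and Grade 2 fix Grade 1 at 60. No operator gives it a usable interval.

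**Step 4: does the toxicity table fill the gap?** SAP Appendix 4, Table 11, has no eGFR row. Its creatinine limit is ≥ 2.6 × the upper limit of the reference range. Assume, for illustration only, that eGFR varies inversely with creatinine. A fall from 120 to 61 then multiplies creatinine by 120/61 = 1.97. A patient who starts at or below the upper limit ends at no more than 1.97 times that limit, below 2.6, and is not flagged as toxicologically high. The normal-range table for creatinine would show a shift only if the value crossed the upper limit.

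**Step 5: the source of the value.** The protocol's schedule of assessments takes height at Visits 1 and 9 only, and Protocol 9.2.7 allows an estimate. Biochemistry is also drawn at Visits 5, 6 and 7, and at Visit 8 for patients on valproic acid. A height-based formula therefore needs a rule for which height applies at Visits 5 to 8.

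**The case against.** The strongest reply is that nothing need be lost. SAP 9.2.1 summarises change and percentage change by visit for each laboratory parameter, so a fall from 120 to 61 would contribute −49% there. It calls the eGFR table separate and does not say that it replaces the normal-range table. If the laboratory supplies an eGFR range, a value below it would be Low in that table. Creatinine has its own summaries and shift tables, and all laboratory data are listed. This stands, and it limits the point to one display.

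A second reply is that SAP 6.1.9 lets additional derived variables unrelated to the primary or secondary endpoints be documented in the programs without amending the SAP. That could cover an eGFR formula. It does not cover the grade limits, which are printed and would be programmed as they are.

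Third, the documents give no lower limit of normal for eGFR. They do not show that values just above 60 are abnormal, and if the laboratory's limit is 60 then nothing above 60 is misfiled. That stands too. It bears on where the new cut-point belongs; it does not give Grade 1 any width.

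A reader might go further and infer that the plan hides renal decline, that these grades act as a safety threshold, or that mild decline is the change most likely to be seen in 24 weeks. The documents support none of these. The other outputs could show the decline. No discontinuation or reporting rule uses eGFR grades; the laboratory-specific criteria in Protocol 10 and 12.8 concern the liver. Nothing is said about expected renal change. An expected count for Grade 1 cannot be given either, since no eGFR distribution is stated.

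**Conclusion.** The point holds as a minor defect. The finding on the limits is certain because it follows from the printed values alone: Grade 1 is one point, the five-level scale works as four, and the separate eGFR shift table records any fall that stays above 60 as no change. Its reach is small. One descriptive safety table is affected, in a discontinued trial whose SAP (sections 1, 8 and 9.5) plans no inferential analysis. That the decline could be seen elsewhere assumes that eGFR is handled like any other laboratory parameter and, for the normal-range table, that the laboratory supplies a range. The missing statement of the eGFR source is a related gap of similar weight.

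**What to change.** 1. Give Grade 1 a real interval and set the bound of Normal to match. One option is Normal at or above the central laboratory's lower limit of normal, Grade 1 from 60 to below that limit, and Grades 2 to 4 unchanged. First confirm that the limit is above 60. If it is 60, this Grade 1 would be empty, and the sponsor should choose and justify another boundary or drop the grade.
2. State the source of the graded value. Either grade the collected creatinine clearance, after confirming that it is reported per 1.73 m² as the grades require, or name the eGFR formula. If the formula uses height, say which height applies at Visits 5 to 8 and how estimated heights are treated.

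The cost is a few lines of SAP text and programming. No new assessment is needed, though a height-based formula would rest on heights taken only at Visits 1 and 9.

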6.2 Exclusion Criteria

The patient may not enter the trial if ANY of the following apply:

- 6.2.1 Patient meets exclusion criteria for RTT diagnosis (traumatic brain injury, neurometabolic disease, or severe infection that causes neurological problems; grossly abnormal psychomotor development in the first 6 months of life).
- 6.2.2 Patient has clinically significant abnormal laboratory values, in the investigator's opinion.
- 6.2.3 Patient experiences more than weekly seizures (based on history over the last 2 months prior to screening) i.e., CSS 'epilepsy/seizure' score of 4 or 5.
- 6.2.4 Patient is taking more than 2 concurrent AEDs.
- 6.2.5 Any history of suicidal behavior or any suicidal ideation in the last month or at screening.
- 6.2.6 Patient has clinically relevant abnormalities in the ECG measured at screening or randomization (including QT interval, corrected by Bazett's correction formula [QTcB] interval > 450 msec, average of 3 measurements).
- 6.2.7 Patient has any concurrent cardiovascular conditions which will, in the investigator's opinion, interfere with the ability to assess the patient's ECGs or put the patient at risk because of participation in the trial.
- 6.2.8 Patient's first or second degree relative has a history of significant ECG abnormalities, in the opinion of the investigator (e.g., premature cardiac arrest, sudden death).
- 6.2.9 Patient has any known or suspected hypersensitivity to cannabinoids or any of the excipients of the IMP (active or placebo), such as sesame oil.
- 6.2.10 Patient has moderately impaired hepatic function at screening, defined as serum ALT or AST $> 3 \times$ ULN **or** total bilirubin [TBL] $> 2 \times$ ULN.

Study Code: GWND18064

EudraCT Number: 2018-003370-27

Clinical Protocol 4.1, 07Jul2020 (duplicate synopsis removed)

6.2.11 Female patient is of childbearing potential, unless willing to ensure that they or their partner use a highly effective method of birth control (e.g., combined [estrogen and progestogen containing], hormonal contraception^a associated with inhibition of ovulation [oral, intravaginal or transdermal], progestogen-only hormonal contraception^b associated with inhibition of ovulation [oral, injectable or implantable]^b, intrauterine devices/hormone-releasing systems^b, bilateral tubal occlusion^b, vasectomized partner^{b,c}, sexual abstinence^d) during the trial and for 3 months thereafter.

6.2.12 Female patient is pregnant (positive pregnancy test) or lactating.

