8.2 Concomitant Therapy

It is theoretically possible that GWP42003-P may modify the metabolism of other drugs (including AEDs) administered concurrently and there remains the possibility of pharmacological interactions between GWP42003-P and other concurrently administered drugs. Doses of any concomitant medications for RTT-related symptoms (including AEDs) must have been stable for at least 4 weeks prior to screening and should be expected to remain stable throughout the trial period. If there are side-effects suspected of being related to an elevation in the concomitant concentration, the investigator should contact the GW medical monitor to discuss best management. Decisions should be based on clinical symptoms and not plasma levels of concomitant medications. The final decision regarding dose adjustments should be taken by the investigator. CBD has the potential to induce the expression of hepatic cytochrome P450 (CYP450) enzymes (CYP1A2, 2B6 and 3A4) at clinically relevant concentrations. Careful titration of CBD in patients taking concomitant medications metabolized by CYP3A4, CYP2C19 or CYP2B6 is advised, with plasma monitoring of such medications or their metabolites to be undertaken at the investigator's discretion. Further information on drug interactions can be found in the IB⁶⁴. Concomitant medication dose reductions are permitted on clinical grounds (e.g., due to AEs or transaminase elevations not meeting IMP discontinuation

Study Code: GWND18064

EudraCT Number: 2018-003370-27

Clinical Protocol 4.1, 07Jul2020 (duplicate synopsis removed)

criteria specified in [Section 10](#) and [Section 12.8](#)). Dose adjustments should be discussed with the GW medical monitor. Any concerns regarding potential interactions with concomitant medications can be discussed with the trial medical monitor(s).

Any non-pharmacological interventions (e.g., physical therapy, speech therapy, dietary supplements, probiotics etc.) must also be stable for 4 weeks prior to screening and the patient/caregiver must be willing to maintain a stable regimen throughout the trial.

The use of rescue medication is allowed when necessary (i.e., AED for transient exacerbation of seizures). Any medication, other than the IMP, taken during the trial must be recorded on the electronic case report form (eCRF).

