9.2.6 Concomitant Medication

Details of all current and recent medication (i.e., taken within the previous 14 days of the screening visit) will be recorded at Visit 1. All medications or interventions for RTT related symptoms used during the trial, including AEDs, should have been maintained at a stable dose over a period of 4 weeks prior to screening and patients and their caregivers must agree to maintain these at a stable dose throughout the duration of the trial; however concomitant medications may be changed if required in response to a safety concern. Any changes in concomitant medication during the trial must be recorded on the eCRF at trial visits. Patients should stop taking any prohibited therapy prior to the screening visit, as defined in [Section 8.3](#). The timing of concomitant medications will be collected on PK sampling visits ([Section 9.2.12](#)).

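### The SAP's only AED-count subgroups for liver enzymes (3 or more, 4 or more) lie above the protocol's entry limit of 2 AEDs, and the counts expected in this population are not tabulated

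*SAP*

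**What the plan says.** SAP 9.2.1 plans a table of patients whose ALT, AST or either transaminase exceeds set multiples of the upper limit of normal, including the combination with raised bilirubin or INR. It is produced overall and for five subgroup lines. Three concern named drugs: valproic acid (yes/no), clobazam (yes/no), and the four combinations of the two. The other two concern AED number: "Patients taking 3 or more current AEDs" and "Patients taking 4 or more current AEDs".

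For the named drugs the SAP gives a time rule: "A medication will be considered concomitant if it has a start date on or after the first dose of IMP", or if it was started earlier and was ongoing. The AED-count lines use the word 'current' instead, which is not defined. They also name one side only; there is no group below 3.

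The protocol limits AED number at entry. Criterion 6.2.4, repeated in the synopsis, excludes a patient if "Patient is taking more than 2 concurrent AEDs".

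**The concern.** Both cut-offs exceed the largest number of AEDs an eligible patient can be taking at entry. Other protocol rules work against the number rising later. Treatment for Rett-related symptoms must be stable before screening and kept stable (6.1.9, 8.2), new medication for such symptoms is prohibited (8.3), and patients with more than weekly seizures are excluded (6.2.3).

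Two consequences follow. The table cannot compare liver-enzyme elevations by AED number over the range that exists in this population, because 0, 1 and 2 are pooled in the overall column. And the patients who do reach the 3-or-more line get there mainly through an event after randomization or a deviation, so the line does not describe background co-medication. A seizure exacerbation that leads to a rescue AED may itself depend on the assigned treatment.

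**Working it through.** The plan states no expected size for these subgroups, so there is no figure to reproduce. The check compares the rules and then adds an illustrative count.

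**Step 1: at entry.** The maximum under criterion 6.2.4 is 2. The SAP cut-offs are 3 and 4. Read as a baseline count, both subgroups contain eligibility deviations only.

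**Step 2: routes to a third AED after entry.**
- Rescue (Protocol 8.2) is permitted: "The use of rescue medication is allowed when necessary (i.e., AED for transient exacerbation of seizures".
- Safety (Protocol 9.2.6): "concomitant medications may be changed if required in response to a safety concern".
- Prohibited additions (Protocol 8.3): a patient who takes one is not normally taken off treatment.
- Deviations (SAP 5, Safety Analysis Set): every dosed patient is kept, including anyone randomized in breach of 6.2.4.

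So 2 at baseline + 1 added = 3 puts a patient in the first subgroup, and 2 + 2 = 4 in the second. The 4-or-more group lies inside the 3-or-more group and cannot be larger.

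**Step 3: how many.** Planned sizes are 84 per active arm and 252 in total (Protocol 13.1). The documents give neither the share of patients on 2 AEDs (*f*) nor the share of those who add one (*r*). Both ranges below are assumptions.

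Expected number with 3 or more = N × *f* × *r*. Chance of at least one in an arm = 1 − (1 − *f* × *r*)^84.

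| *f* | *r* | Expected per 84 | Expected per 252 | Chance of at least one in 84 |
|---|---|---|---|---|
| any | 0 | 0 | 0 | 0 |
| 0.10 | 0.05 | 0.42 | 1.26 | 0.34 |
| 0.10 | 0.20 | 1.68 | 5.04 | 0.82 |
| 0.30 | 0.05 | 1.26 | 3.78 | 0.72 |
| 0.30 | 0.20 | 5.04 | 15.12 | 0.99 |

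The count leaves out eligibility deviations and patients who start on 0 or 1 AED and add several. It uses planned numbers; SAP 9.5 says the trial was discontinued, and the documents do not give the number randomized.

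**Step 4: what such a group could show.** At the top of the range, about 5 patients in an arm, a single patient with an elevation moves the percentage by 1/5 = 20 points.

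**Step 5: dependence on the undefined word.** If 'current' means at first dose, only deviations qualify. If it means at any time on treatment, on-study additions count as well. Whether one rescue dose makes an AED current is also not stated. Two programmers could produce different tables from the same data.

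**The case against.** The strongest reply is that the entry criterion does not govern AED use on treatment, and Step 2 shows several routes to 3 or more. This stands. A reader might infer from the mismatch that the subgroups are empty by design and every cell is zero. The documents do not support that; under most of the assumed combinations at least one such patient per planned arm is more likely than not.

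A second reply is that the liver risk factor the protocol singles out is valproic acid, not AED number. Protocol 3.2.2 names it, 3.3.3 expects lower risk partly because its use should be lower here, and Visit 8 laboratory samples are taken only from patients receiving it (9.1.1.6). SAP 9.2.1 analyzes it directly, together with clobazam. This also stands. A reader might conclude that the whole AED safety analysis is lost, or that the trial cannot show whether AED use bears on liver risk. That goes too far: three of the five subgroup lines are untouched by the entry limit.

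A third reply is that little depends on the two lines. The analysis is descriptive with no hypothesis testing (SAP 8), every treated patient appears in the overall summary, liver parameters and medications are listed, and SAP 1 allows labelled post-hoc work. This limits the importance of the point but does not answer it: a reader would have to rebuild a simple tabulation from listings, while the planned one is sparse and has an ambiguous definition.

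**Conclusion.** The point holds as a minor one. The 3-or-more and 4-or-more AED lines do not fit a population limited to 2 AEDs at entry. They can be filled only by eligibility deviations or AEDs added on study, and will probably be empty or very sparse: 0 with no additions, and about 0.4 to 5.0 patients per planned arm of 84 under the assumed ranges. What is lost is a view of transaminase elevations by AED number over 0, 1 and 2. No efficacy result or formal inference is affected.

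The mismatch in cut-offs and the undefined term rest on the documents alone. The degree of sparseness rests on assumed AED use and would change with the actual medication data.

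**What to change.** Replace the two AED-count lines in SAP 9.2.1 with:

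- 0, 1 and 2 AEDs ongoing at the first dose of IMP.
- More than 2 AEDs, at baseline or at any time on treatment, as a separate category or listing. State whether the patient was above 2 at baseline (an eligibility deviation) or got there on study. Do not merge these patients into the stratum for 2, which would hide the most heavily co-medicated patients.

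A patient on 2 AEDs at first dose who later takes a third stays in the baseline stratum and also appears in the separate display; a footnote should say so. Define which drugs count as AEDs and whether rescue doses count. Keep the valproic acid, clobazam and combined subgroups as they are.

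The cost is a short SAP edit and minor reprogramming. Concomitant medications are already recorded on the eCRF (Protocol 8.2, 9.2.6), so no new data are needed. If the tables have already been run, the same display can be added and labelled post hoc under SAP 1.
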